4.2 Secondary variables

The following secondary variables will be measured:

- Retention on LCM at the end of the 6-month Observation Period
- Time to discontinuation of LCM treatment from the date of first dose of LCM
- Change from Visit 1 (Baseline) to Visit 3 (Month 6 or end of Observation Period) in the 5-Level EuroQol-5 Dimension Quality of Life Assessment (EQ-5D-5L) visual analogue scale (VAS) score and change in utility as converted from the 5 dimensions
- Change from Visit 1 (Baseline) to Visit 3 (Month 6 or end of Observation Period) in the M.D. Anderson Symptom Inventory - Brain Tumor (MDASI-BT)
- Actual change from Visit 1 (Baseline) to Visit 3 (Month 6 or end of Observation Period) in seizure frequency (seizures per 28 days)
- Percentage change from Baseline in seizure frequency
- Seizure-free status (Yes/No) at the end of the 6-month Observational Period
- Discontinuation rate of LCM due to adverse drug reactions (ADRs)
- Discontinuation rate of LCM due to lack of effectiveness
- Clinical Global Impression of Change (CGIC) rating at Visit 3 (Month 6 or end of Observation Period)

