15 RECOMMENDED SCHEDULE OF STUDY ASSESSMENTS

Table 15–1: Recommended schedule of study assessments

Assessments	Visit 1 ^a (Baseline)	Visit 2 Approximately 3 months after Baseline according to routine practice ^b	Visit 3 (End of Observation Period or Withdrawal Visit ^c) Approximately 6 months after Baseline according to routine practice ^b
Signed data consent	X		
Demographic data	X		
Medical history	X ^d		
Seizure history	X ^d		
Tumor diagnosis and grade (including review of most recent brain imaging results [CT or MRI])	X		X
Prior and concomitant tumor management (surgical procedures, chemotherapies, radiotherapy)	X ^d		X
Prior and concomitant AEDs	X	X	X
Other prior and concomitant epilepsy treatment	X	X	X
Other prior and concomitant relevant medications	X ^d	X	X
Verification of selection criteria	X		
Documentation of LCM administration	X	X	X
Documentation of seizure information (including seizure frequency and type) ^e		X	X
Karnofsky performance status	X	X	X
EQ-5D-5L	X		X

Table 15–1: Recommended schedule of study assessments

Assessments	Visit 1 ^a (Baseline)	Visit 2 Approximately 3 months after Baseline according to routine practice ^b	Visit 3 (End of Observation Period or Withdrawal Visit ^c) Approximately 6 months after Baseline according to routine practice ^b
MDASI-BT	X		X
PGIC			X
CGIC			X
Recording of ADRs and AESIs	X	X	X
Withdrawal criteria		X	X

ADR=adverse drug reactions; AED=antiepileptic drug; AESI=adverse event of special interest; CGIC=Clinical Global Impression of Change; CT=computerized tomography; EQ-5D-5L=5-Level EuroQol-5 Dimension Quality of Life Assessment; LCM=lacosamide; MRI=magnetic resonance imaging; MDASI-BT=M.D. Anderson Symptom Inventory - Brain Tumor; PGIC=Patient Global Impression of Change

^a Visit 1 will be performed after the decision is taken to start adjunctive LCM therapy. Treatment with LCM should be initiated according to routine clinical practice. If the first dose of LCM is given on the same day as Visit 1, it should be administered after Baseline assessments are complete. Previous treatment with LCM is allowed for up to 7 days prior to enrollment.

^b The frequency of visits after Visit 1 will be based on local clinical practice and the patients' requirements. The clinical procedures performed at each visit will also follow local clinical practice. It is estimated that patients will be followed at least every 3 months.

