^c Patients who discontinue early should perform Visit 3 assessments as a Withdrawal Visit.

^d During the previous 8 weeks and relevant information in the past according to the physician's decision.

^e The treating physician will evaluate at each visit, as part of standard practice with the patient, the frequency and type of seizures experienced by the patient since the previous study visit.

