3.2 General study level definitions

3.2.1 Analysis time points

The following visits are recommended documentation time points and will be considered for analysis. Due to the nature of a NIS, the time points given for each visit are approximated, expected time points only.

- Visit 1, Baseline
- Visit 2 (approximately 3 months after Baseline): Visits that occurred \leq 135 days after Visit 1
- Visit 3 (approximately 6 months after Baseline or Withdrawal Visit for patients who discontinue early): All visits that occurred $>$ 135 days after Visit 1

If there are 2 visits that meet the criteria for Visit 2, then the visit nearest to the scheduled assessment time for Visit 2 will be used (i.e. 90 days after Visit 1). If there are 2 visits that meet the criteria for Visit 3, then the visit nearest to the scheduled assessment time for Visit 3 will be used (i.e. 180 days after Visit 1). No different study periods will be considered for this NIS.

However, the period for the analysis of safety variables is defined as follows:

- Observational Period: The Observational Period starts with the start date of LCM and ends at the day of study termination. In case the start date of LCM is missing, the date of Visit 1 will be used instead.

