3.10.4 Seizure Frequency

Partial-onset seizure frequency per 28 days will be derived from the number of days in the considered time interval (D) for which seizure information was provided:

$$(\text{Number of seizures over the specified time interval}) \times (28/D)$$

The considered time interval is defined as 56 days for the historical seizure count at Baseline (8 weeks x 7 days) and as date of actual visit – date of previous visit for all other time points. Note

if any subjects have a diagnosis of epilepsy less than 8 weeks prior to study entry, then site will be instructed to give their best approximation of the 8-week seizure frequency and the reported historical seizure count will be assumed to be representative of the full 8 weeks. The seizure frequency per 28 days cannot be derived using the time from diagnosis of epilepsy to study start as the time period for reporting the historical seizure frequency for such subjects because only the month and year are collected for the date of diagnosis.

The absolute and percentage change in partial-onset seizure frequency from Baseline (Visit 1) will be derived for Visit 2 and Visit 3.

A responder is defined as a patient who experiences a 50% or greater reduction in partial-onset seizure frequency from Visit 1 (Baseline) to Visit 3 (Month 6 or end of Observation Period).

The seizure-free status (Yes/No) at the end of the 6-month Observation Period will be determined for each patient. A patient is seizure-free if the seizure count at Visit 3 (Month 6 or end of the Observation Period) is 0, otherwise the patient is not seizure-free at the end of the 6-month Observation Period.

The frequency of seizures with and without secondary generalization will also be calculated based upon the response to the question 'Number of partial-onset seizures with secondary generalization' in the CRF. If the number with secondary generalization is known, the number of seizures with secondary generalization will be taken from the CRF and the number of seizures without secondary generalization will be calculated as overall number of seizures – number of seizures with secondary generalization.

Partial-onset seizure frequency per 28 days at a dose of <200mg/day at Visit 2 and Visit 3 will be derived from the number of days in the considered time interval (D) for which seizure information was provided where the subject was on a dose of <200mg/day according the dosing log for LCM:

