8.2.6 Seizure-free status

The number and percentage of patients achieving a seizure-free status (Yes/No) at the end of the 6-month Observation Period will be presented. Percentages are based on the number of patients with available data. A 2-sided 95% CI (calculated using the 2-sided Clopper-Pearson method) for the percentage of patients achieving a seizure-free status (Yes/No) will be presented.

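### Seizure-free status rests on the Visit 3 count alone, so a patient with seizures recorded at Visit 2 can count as seizure-free, and the percentage is reported without its interval or a whole-period rate beside it

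*SAP*

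**What the plan says.** **The variable.** Protocol 4.2 lists "Seizure-free status (Yes/No) at the end of the 6-month Observational Period" as a secondary variable. SAP 3.10.4 makes it operational: "A patient is seizure-free if the seizure count at Visit 3 (Month 6 or end of the Observation Period) is 0"; any other count means not seizure-free.

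**What the count covers.** SAP 3.10.4 sets the interval at 56 days for Baseline and as "date of actual visit – date of previous visit for all other time points". Footnote e of protocol Table 15-1 has the physician evaluate "the frequency and type of seizures experienced by the patient since the previous study visit".

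**What is reported.** SAP 8.2.6: "The number and percentage of patients achieving a seizure-free status (Yes/No) at the end of the 6-month Observation Period will be presented", with a Clopper-Pearson 95% CI. On the denominator: "Percentages are based on the number of patients with available data". SAP 8.1.2.1 and 8.1.2.2 use the same denominator rule for response and PGIC.

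**Visit timing.** Footnote b of Table 15-1: "The frequency of visits after Visit 1 will be based on local clinical practice". SAP 3.2.1 assigns visits up to and including day 135 to Visit 2 and later ones to Visit 3, with no minimum gap between them. If two visits qualify as Visit 3, the one nearest day 180 is kept.

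**Withdrawal visits.** The SAP 3.2.1 definition begins "Visit 3 (approximately 6 months after Baseline or Withdrawal Visit for patients who discontinue early): All visits that occurred" and goes on to require more than 135 days after Visit 1. Table 15-1 puts the Withdrawal Visit in the Visit 3 column. SAP 2.3 asks early discontinuers for the Visit 3 assessments at that visit, and SAP 3.2.2 uses it to close the Observational Period.

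**The concern.** A single percentage with a confidence interval, printed beside the words 6-month Observation Period, is easily read as the share of patients free of seizures for six months. As defined, it can include patients whose Visit 2 record shows seizures on study. Seizure frequency is scaled to 28 days and so allows for interval length. A zero count is not scaled, and zero is easier to reach over a short interval. The by-visit frequency summaries in SAP 8.2.5 do not let a reader recover a whole-period seizure-free percentage.

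The Withdrawal Visit question is separate and reaches further. A patient needs only one post-Baseline assessment to enter the FAS (SAP 3.5.3). If a withdrawal by day 135 is classed by day, that patient is in the FAS but has no Visit 3 value, and so leaves the available-data percentages for response, PGIC and seizure freedom. The recorded reasons for early termination include lack of efficacy and adverse drug reaction (SAP 3.10.10 to 3.10.12), so the omission can favour the drug.

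**Working it through.** **1. The plan's own figure.** The documents give no expected seizure-free rate. Their only sample-size figure concerns the responder rate: 1.96² × 0.6 × 0.4 / 0.10² = 92.2, rounded up to 93, with half-width 0.0996 at n = 93. It reproduces and is not affected by this point.

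**2. Reading the definition.** Status depends on the Visit 3 count, and the count starts at the previous visit. Visit 2 seizures therefore do not enter, and no other section adds them back. The exception is a patient with no Visit 2, whose Visit 3 count runs from Visit 1.

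**3. Interval lengths that the rules allow** (possible cases, not expected frequencies). The last column assumes a constant Poisson rate of 1 seizure per 56 days, the entry minimum in protocol 8.1.

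| Visit 2 day | Visit 3 day | Interval (days) | Chance of a zero count |
|---|---|---|---|
| 135 | 136 | 1 | 98.2% |
| 135 | 180 | 45 | 44.8% |
| 90 | 136 | 46 | 44.0% |
| 90 | 180 | 90 | 20.0% |
| 30 | 180 | 150 | 6.9% |
| none | 180 | 180 | 4.0% |

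Two visits after day 135 can go either way. With visits at days 90, 136 and 180, day 180 is kept and its count may cover only 180 − 136 = 44 days. With visits at days 90, 175 and 200, day 175 is kept, its count runs from day 90, and seizures in days 175 to 200 are ignored.

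**4. Last interval against whole period.** Assumptions: visits at days 90 and 180, and rates r of 0.25, 0.5 and 1 per 56 days, the same in both intervals. The mean count over D days is m = r × D/56. For a constant rate, P(0) = exp(−m). If rates vary between patients (gamma-Poisson, shape k), P(0) = (1 + m/k)^(−k). For D = 90 and 180, m is 0.402 and 0.804 (r = 0.25), 0.804 and 1.607 (r = 0.5), and 1.607 and 3.214 (r = 1). Gaps are taken before rounding. The last column is 1 − P(0 in 180 days)/P(0 in 90 days).

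| Model | r | Last 90 days | All 180 days | Gap (points) | Labelled seizure-free but with an earlier on-study seizure |
|---|---|---|---|---|---|
| Constant | 0.25 | 66.9% | 44.8% | 22.1 | 33% |
| Constant | 0.5 | 44.8% | 20.0% | 24.7 | 55% |
| Constant | 1 | 20.0% | 4.0% | 16.0 | 80% |
| k = 1 | 0.25 | 71.3% | 55.4% | 15.9 | 22% |
| k = 1 | 0.5 | 55.4% | 38.4% | 17.1 | 31% |
| k = 1 | 1 | 38.4% | 23.7% | 14.6 | 38% |
| k = 0.5 | 0.25 | 74.5% | 61.9% | 12.5 | 17% |
| k = 0.5 | 0.5 | 61.9% | 48.7% | 13.2 | 21% |
| k = 0.5 | 1 | 48.7% | 36.7% | 12.0 | 25% |

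**5. Mixing intervals.** If a share f of patients miss Visit 2, the pooled percentage falls by f × gap. For a constant rate and k = 1, f = 0.1 gives 1.5 to 2.5 points (for example 0.1 × 22.1 = 2.2), and f = 0.2 gives 2.9 to 4.9.

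**6. Withdrawal visits by day 135.** The documents give no expected number, so this is illustration only, on 93 FAS patients. Suppose 10 withdraw by day 135 and 50 of the other 83 respond. Classed by day, the responder rate is 50/83 = 60.2%. Classed as Visit 3, it is 50/93 = 53.8% if none of the 10 responds, or 53/93 = 57.0% if three do. With 5 withdrawals and none responding it is 53/88 = 60.2% against 53/93 = 57.0%; with 20, 44/73 = 60.3% against 44/93 = 47.3%. There is no difference if those who withdraw respond as often as the rest.

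**The case against.** The definition and the label agree. Every statement of the endpoint speaks of status at the end of the period. The interval is the one used for the primary responder variable, so seizure freedom is simply a 100% reduction over that interval. SAP 3.10.4 states the interval. All efficacy data are listed (SAP 8.1) and Visit 2 frequency is summarised, so earlier seizures are not hidden. The sizes rest wholly on assumed rates held constant across both intervals, although the first includes titration. Nothing is tested.

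Most of this stands, and it rules out several stronger readings that a reader might reach:

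- *That the plan claims six months of seizure freedom.* It does not; the wording is status at the end.
- *That no interval is defined.* It is, in SAP 3.10.4. It varies in length and is not attached to the percentage in SAP 8.2.6.
- *That the kept visit always counts from another visit after day 135.* This is so only when the later of two such visits is kept.
- *That most patients labelled seizure-free would have had earlier seizures.* The 80% figure needs no improvement from the entry minimum and no variation between patients. With variation the share is 17% to 38%.

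The objection does not supply a whole-period percentage, and it does not tell the reader of SAP 8.2.6 which interval the figure describes. Nor does it settle the Withdrawal Visit conflict. SAP 2.3 can be read as an instruction on what to collect, and SAP 3.2.2 can be read either way, but SAP 3.2.1 contradicts itself and the Table 15-1 column sides with Visit 3.

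**Conclusion.** The point holds as one of reporting and completeness. The variable is consistent with its name, but the percentage can include patients with seizures recorded on study, pools intervals of different length, and stands without a whole-period rate. Under the assumptions in the working it exceeds a whole-period rate by 16 to 25 points with a constant rate, 15 to 17 with shape 1 and 12 to 13 with shape 0.5. Mixed intervals from a missed Visit 2 matter less, at about 1.5 to 5 points. The consequence is a misread secondary, descriptive rate; no test or sample size is affected.

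The Withdrawal Visit conflict is a separate defect and weighs more, because it decides who is in the denominator of both primary variables. Its direction favours the drug only if early withdrawals do worse than the rest, which is plausible given the recorded reasons but not established by the documents.

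**What to change.** 1. **SAP 8.2.6.** Keep the protocol variable and its name, state that it covers the time since the previous visit, and report the distribution of interval lengths.
2. **Supportive rate.** Add one percentage with Clopper-Pearson CI that requires zero seizures in every post-Baseline count from Visit 1 to Visit 3, including visits not selected under SAP 3.2.1. Base it on completers whose counts cover the whole period. Apply the coverage rule whether or not a seizure was recorded, so that coverage does not depend on outcome, and report how many completers lack coverage. A missed Visit 2 is not a gap if the Visit 3 count runs from Visit 1. A labelled sensitivity row counting non-completers as not seizure-free is optional.
3. **Visit assignment.** Reconcile protocol Table 15-1 with SAP 2.3, 3.2.1 and 3.2.2 on which analysis visit a Withdrawal Visit on or before day 135 belongs to. Apply the answer to response, PGIC and seizure-free status alike. If it is Visit 3, short intervals enter the seizure-free percentage, which is a further reason to report interval lengths.

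**Cost.** SAP wording, one added flag and one or two table rows, with no new data and no protocol change to the variable. Downsides to state: the whole-period rate includes titration and will be lower; it starts at Visit 1, which may be up to 7 days after the first LCM dose or some time before it; completers are a selected group; and the sensitivity row departs from the available-data rule.

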3.10.5 Patient Global Impression of Change

Patients will be categorized based on their PGIC value collected at Visit 3 into the following groups:

- Improved: scores 1 to 3
- No change: score 4
- Worsened: score 5 to 7

3.10.6 Retention rate

The 6-month retention rate is the percentage of patients remaining in the study and on LCM treatment for 6 months. This will be estimated using Kaplan-Meier methodology applied to the time to discontinuation of LCM. A cut of 180 days will be used for 6 months. The derivation of the time to discontinuation and the corresponding censoring flag are described in Section 3.10.7.

3.10.7 Time to discontinuation of LCM

Time to discontinuation of LCM will be defined as

The date of last administration of LCM while in the study - the date of first dose of LCM + 1

If the date of last administration of LCM while in the study is not available the study termination date will be used. If the start date of LCM is missing, then it is assumed that the patient did not receive treatment and they would be consequently excluded from the relevant analysis sets and therefore from this analysis.

A censor flag will be derived where patients who completed the study are censored and patients who have discontinued LCM prior to the end of the 6-month Observation Period (early withdrawals) are not censored.

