8 SELECTION AND WITHDRAWAL OF PATIENTS

8.1 Selection criteria

Before any data are collected for any patient in this NIS, written data consent will be properly executed and documented.

The following selection criteria must be followed for patients entering the NIS:

1. Patient has never been treated with LCM prior to this NIS or treatment with LCM for the first time started no earlier than 7 days prior to enrollment in this NIS.
2. The decision by the treating physician to prescribe LCM falls within current standard clinical practice, and the treatment decision is clearly separated from the decision to consider inclusion of the patient in the NIS.
3. A Patient Data Consent form is signed and dated by the patient and/or by the parent(s) or legal representative.
4. Patient is a male or female ≥ 16 years of age.

5. Patient must have a diagnosis of BTRE secondary to low-grade glioma (World Health Organization Grade 1 to 2 at time of enrollment).
6. Patient has a retrospective Baseline seizure frequency of at least 1 partial-onset seizure in the 8 weeks prior to start of LCM treatment.
7. Patient does not have a previous diagnosis of epilepsy before tumor onset.
8. Patient does not have brain metastases.
9. Patient has a Karnofsky performance status scale index $\geq 60\%$.
10. Patient is currently taking only 1 or 2 Baseline AEDs for epilepsy other than LCM.
11. Patient has received a maximum of 4 different lifetime AEDs ever before entering the NIS.

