8.2.1 Retention rate

Retention rate is defined as the percentage of patients remaining in the study and on LCM treatment for 6 months (6-month retention rate). The number of patients remaining in the study and on LCM treatment for 6-months will be summarized with the retention rate in the SS, the FAS and the modified FAS. The retention rate will be derived using Kaplan-Meier methodology where patients who remain on treatment at the end of the 6-month Observation Period are censored at the date of last administration of LCM. A 2-sided 95% CI (based on Greenwood's formula) for the 6-month retention rate will be presented.

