8.2.7 Discontinuation of LCM due to an ADR

The number and percentage of patients who discontinue LCM due to an ADR will be presented for the SS, the FAS and the modified FAS. A 2-sided 95% CI (calculated using the 2-sided Clopper-Pearson method) for the percentage of patients who discontinue LCM due to an ADR will be presented.

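### Patients may enrol after up to 7 days on lacosamide, but retention and time to discontinuation use ordinary Kaplan-Meier from first dose with no delayed entry, a small bias that can only be upward

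*SAP*

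**What the plan says.** **Entry.** Protocol 8.1, criterion 1, admits patients never treated with LCM and also those whose "treatment with LCM for the first time started no earlier than 7 days prior to enrollment in this NIS". Footnote a of Table 15-1 (Protocol 15) repeats it: "Previous treatment with LCM is allowed for up to 7 days prior to enrollment".

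**Time origin.** SAP 3.10.7 defines time to discontinuation as "The date of last administration of LCM while in the study - the date of first dose of LCM + 1". No entry time is defined. On censoring it says: "A censor flag will be derived where patients who completed the study are censored"; early withdrawals are events.

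**Estimator.** For 6-month retention, SAP 3.10.6 says: "This will be estimated using Kaplan-Meier methodology applied to the time to discontinuation of LCM", and "A cut of 180 days will be used for 6 months". SAP 8.2.1 says the same: "The retention rate will be derived using Kaplan-Meier methodology where patients who remain on treatment at the end of the 6-month Observation Period are censored". SAP 8.2.2 uses the same times for the median and the plots.

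**Related crude rate.** SAP 8.2.7: "The number and percentage of patients who discontinue LCM due to an ADR will be presented for the SS, the FAS and the modified FAS".

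**Where pre-starters are set apart.** SAP 3.10.9 and 8.2.4 (MDASI-BT) and 8.2.3 (EQ-5D-5L) restrict change scores to patients with an evaluable Baseline, meaning in practice patients not yet on LCM at Visit 1. No such separation appears for retention, time to discontinuation or discontinuation due to an ADR, nor among the subgroups in SAP 4.8.

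**The concern.** A patient who starts LCM and stops it before enrolling does not get into the analysis. The Safety Set (SAP 3.5.2) requires LCM taken within the study, Protocol 8.1 allows no data collection before consent, and no log of such patients is described. A patient who enrols while already on LCM has, by that fact, stayed on it until Visit 1. Timing from first dose with an ordinary risk set gives this patient up to 7 days at risk in which an event was impossible, while the matching early stops are absent. This is left truncation.

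Protocol 17.1 and SAP 14.1 show how it arose. Visit 1 used to precede the first dose, so an ordinary risk set from first dose was then sound. The amendment removed that condition and the risk set was not adapted.

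At stake are two listed secondary variables, retention and time to discontinuation. The crude percentage discontinuing because of an ADR is subject to the same selection, in the direction of understatement.

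**Working it through.** **The plan's own figure.** The documents give no expected retention rate and no precision for it. The only stated precision is for the responder rate (Protocol 11.5, SAP 2.4). It reproduces: 1.96² × 0.60 × 0.40 / 0.10² = 92.2, rounded up to 93; half-width at n = 93 is 1.96 × √(0.24/93) = 0.0996; 93/0.93 = 100 enrolled.

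**Inputs for the bias.** From the documents: entry up to 7 days after first dose, a 180-day cut, 100 enrolled. Not in the documents, so assumed over a range:
- f, the share of enrolled patients who pre-started: 25%, 50%, 75%
- p, the probability of stopping LCM in week 1: 0.9% to 8%
- retention from day 7 to day 180 among those still on LCM: 80%

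**Upper bound, every pre-starter entering at day 7**, no censoring before day 180:
- Retention from first dose = (1 − p) × 0.80
- As the SAP would estimate it = (1 − f) × (1 − p) × 0.80 + f × 0.80
- Difference = f × p × 0.80

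For p = 5% and f = 50%, retention from first dose is 0.95 × 0.80 = 0.760. The SAP estimate is 0.5 × 0.760 + 0.5 × 0.80 = 0.780, an excess of 2.0 points. The week-1 risk would appear as (1 − f) × p = 2.5% instead of 5%.

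If stopping is no more frequent in week 1 than later (constant hazard), p = 1 − 0.80^(7/173) = 0.9%.

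Excess in 6-month retention (percentage points):

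| Week-1 stopping p | f = 25% | f = 50% | f = 75% |
|---|---|---|---|
| 0.9% (constant hazard) | 0.18 | 0.36 | 0.54 |
| 2% | 0.4 | 0.8 | 1.2 |
| 5% | 1.0 | 2.0 | 3.0 |
| 8% | 1.6 | 3.2 | 4.8 |

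**Entry spread over the week.** Criterion 1 allows entry on any day up to day 7, so the table overstates the effect if entry is earlier. A simulation (100 patients, 600 runs, pre-starters entering uniformly on days 1–7, Visit 3 at 180 days after Visit 1, f = 50%) gave these mean 180-day retention estimates. Here true retention is counted from first dose:

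| True retention | Week-1 stopping | SAP method | Delayed entry | Pre-starters excluded |
|---|---|---|---|---|
| 0.70 | 1.4% (constant hazard) | 0.699 | 0.697 | 0.699 |
| 0.70 | 5% | 0.707 | 0.697 | 0.699 |
| 0.70 | 10% | 0.721 | 0.700 | 0.704 |
| 0.80 | 5% | 0.811 | 0.799 | 0.801 |

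Simulation error is about ±0.4 points. At 5% and half pre-started, the SAP method exceeds delayed entry by about 1.0 to 1.2 points. Delayed entry recovers the true value within that error.

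**Sampling error.** The 95% half-width at n = 100 is 1.96 × √(0.70 × 0.30/100) = 9.0 points at 70% retention and 1.96 × √(0.80 × 0.20/100) = 7.8 points at 80%.

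**Median.** Under constant hazard the shift for a pre-starter equals the lead time, at most 7 days. The median is not reached if 6-month retention exceeds 50%.

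**The case against.** Several arguments on the other side are good.

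- A reader might infer that the first week on LCM goes unrecorded. For enrolled patients that is not so. Protocol 10.1.2 makes ADRs reportable from consent or first administration, whichever is earlier, although its next sentence, on events absent before the initial visit, is less clear. SAP 3.2.1 starts the safety period at the LCM start date, and SAP 3.10.14 takes exposure from first administration using the dosing log. Only patients who stopped and never enrolled are unseen.
- A reader might infer that the main tolerability measures are compromised. SAP 2.2.1.2 lists retention and time to discontinuation as efficacy variables. The safety variables in SAP 2.2.3 are ADRs or AESIs and withdrawal due to ADRs, so only the last overlaps.
- First dose is a legitimate time origin, and the analysis sets are explicitly of enrolled patients. As a plain count of those enrolled, the figure is correct. It then mixes retention from first dose for some patients with retention given survival to Visit 1 for others, and nothing in the SAP says so.
- The effect is probably small, the study is single-arm and descriptive, and no threshold rests on retention. This stands. A confidence interval does not, however, cover a systematic shift.
- Splitting ADR tables by LCM status at Visit 1 cannot bring back patients who never enrolled. This also stands: the pre-starter stratum remains selected.

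**Conclusion.** The point holds as a limited, one-directional bias. The risk set should start no earlier than Visit 1 for pre-starters, and no section of either document provides for that. The bias can only be upward, and patients whose first dose is at or after Visit 1 do not contribute to it.

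Its size cannot be fixed from the documents. Under the stated assumptions it is about 0.2–0.5 points with constant hazard and about 1–2 points with 5% week-1 stopping and half pre-started. The upper end, about 5 points, needs 8% week-1 stopping, 75% pre-starters and all of them entering at day 7. All of this is below the 8–9 point half-width. The documents do not support a conclusion that retention will be materially inflated: that would need both many pre-starters and early stopping concentrated in week 1, and neither is reported. The case for acting is that the correction is cheap and the share of pre-starters would otherwise stay hidden.

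**What to change.** 1. In SAP 3.10.6, 3.10.7, 8.2.1 and 8.2.2, keep first dose as the origin and define an entry time: the later of first dose and Visit 1. Use delayed-entry Kaplan-Meier for retention, the median and the plots. State its assumption that entry time is independent of later stopping.
2. Report the number and percentage of patients already on LCM at Visit 1, with the distribution of their lead days.
3. Add a sensitivity analysis of retention and of discontinuation due to an ADR (SAP 8.2.7) in patients not on LCM at Visit 1.
4. If nearly all patients pre-started, week-1 risk cannot be estimated. Report retention as conditional on still being on LCM at enrolment, and say so in the table title.

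Cost: SAP wording and one derived variable from dates already collected; no new visit, form or procedure. The downside is a slightly less favourable retention figure and smaller risk sets in the first days, which makes the early part of the curve less stable.
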